5.3 EXPLORATORY ENDPOINTS

The exploratory objectives of the study are to evaluate the effect of nalbuphine HCl ER tablets on:

- The potential of nalbuphine HCl ER tablets to impact on the measurement of nerve fiber density (histology) and MOR/KOR density (histology, Western Blot), as well as histological (H&E) changes in skin biopsies taken at Baseline and the final Treatment Period Visit when compared to biopsy material assessed during study TR03 (optional procedure at select sites only).

6 NUMBER OF SITES AND PATIENTS

Up to 20 sites in the North America and Europe are planned to participate in this study. Eligible patients who have successfully completed the TR03 study and wish to participate in TR03ext may be enrolled, treated, and analyzed. The maximum number of patients will not exceed the number of patients who complete the TR03 study (i.e., approximately 60 patients).

7 ESTIMATED STUDY DURATION

The total study duration for any individual patient will be up to 53 weeks. Patients will receive drug treatment for up to 50 weeks, followed by a two week washout period.

8 SELECTION CRITERIA

8.1 STUDY POPULATION

Patients with prurigo nodularis who completed the TR03 study and have met all Inclusion and Exclusion criteria for TR03ext (see [Section 8.2](#) and [Section 8.3](#)).

8.2 INCLUSION CRITERIA

Patients must meet all of the following criteria to be eligible:

1. Have been adequately informed of the nature and risks of the study and have given written informed consent at the conclusion of the TR03 Visit 6 and prior to Visit 1a.
2. Have completed participation in the TR03 study.

Completion of participation in the TR03 study is defined as completion of Study Drug treatment through TR03 Visit 5 and completion of the TR03 Visit 6.

3. Agree to comply with the contraception requirements as below:

Sexually active female patients of childbearing potential are required to use one barrier method (e.g., condom, cervical cap, or diaphragm) of contraception in addition to one other method (e.g., intrauterine device [IUD], hormonal contraception, tubal ligation, Essure procedure, or spermicide).

For the purpose of this study, all females are considered to be of childbearing potential unless they are post-menopausal (i.e., at least 1 year since last menses and age >50 years) or surgically sterile (i.e., tubal ligation, hysterectomy and/or bilateral oophorectomy).

Female patients who are abstinent may participate in the study, however; they must be counseled on the requirement to use appropriate contraception should they become sexually active. This counseling should occur at each study visit and must be documented in source records.

4. Willing and able to comply with study requirements and restrictions.
5. Agree to the confidential use and storage of all data (including photography) and use of all anonymized data for publication including scientific publication.

8.3 EXCLUSION CRITERIA

If a patient meets any of the following criteria, he or she is *not* eligible:

1. Patients with a history of congestive heart failure of Class 2 or higher as graded using the New York Heart Association scale (scale provided in [Appendix 5](#))
2. Patients with a history of angina pectoris grade 2 or higher as graded using the Canadian Cardiovascular Society grading scale (scale provided in [Appendix 5](#))
3. History of ventricular tachycardia, torsade de pointes, family history of sudden death, myocardial infarction or acute coronary syndrome within the previous 3 months, as reported by the patient.
4. Serum potassium below the laboratory lower limit of normality at the TR03 Visit 5. Note: Potassium levels below the laboratory lower limit of normal at Visit 6/Visit 1a should be repeated and potassium supplementation provided as appropriate.
5. QTcF interval >450ms on screening/Visit 1a ECG
6. Heart rate <50 BPM on any screening assessment. Patients with a resting heart rate of <50 bpm will have it repeated once after 5 minutes in the supine position, and if it remains <50 bpm during the repeat, they will be considered a screen failure
7. Use of a medication known to be associated with risk of torsade de pointes (see [Section 9.7.8](#), Safety Assessments, for hyperlink to the CredibleMeds Filtered QTDrug List for cardiovascular related prohibited medications with a known associated risk of Torsade de Pointes)
8. History of substance abuse within the past year as determined by the Investigator
9. Significant medical condition or other factors that in the opinion of the Investigator may interfere with the conduct of the study
10. Known hypersensitivity or allergy to nalbuphine or formulation components
11. Is a pregnant or lactating female.

9 STUDY PLAN

9.1 GENERAL STUDY DESIGN

This is an open label extension study for patients who have completed the TR03 study.

9.2 RATIONALE FOR STUDY DESIGN

The primary objective of this TR03ext study is to evaluate the safety of nalbuphine HCl ER tablets in patients with prurigo nodularis for up to 50 weeks on drug, followed by a two week washout period for a total of up to 53 weeks of study duration. The open label design allows all patients, who have completed the parent study TR03, an opportunity to receive active treatment for the assessment of the safety of nalbuphine HCl ER tablets over a longer term and to follow the effect of skin lesion healing in addition to reducing itch. A maximum of 50 weeks on study drug was chosen as a reasonable time frame that would add substantially to the understanding of chronic use of nalbuphine HCl ER tablets chronic use in prurigo nodularis.

Metze et al (1999) reported that 9 out of 17 patients with PN who were treated with the mu antagonist medication naltrexone reported a decrease in pruritus intensity of at least 50%. Reduced scratching as well as skin lesion healing was reported over a time period of up to 20 months on drug. Based on these clinical observations, TR03ext was designed to be of sufficient duration to observe potential anti-pruritic suppressive effects of study drug on scratching behavior and thus potentially skin lesion healing. Furthermore, the TR03ext study design anticipates potential sustained anti-pruritic effect that may outlast the actual dosing of study drug in TR03. Thus an Observation Period has been incorporated to follow patients whose Worst Itch NRS has been significantly reduced for up to 12 weeks in order to measure the durability of the anti-pruritic effect and to allow patients to receive study drug if pruritus intensity increases within the 12 week time period.

This study will also allow evaluation of a titration algorithm that mimics the manner in which opioid medications are often used in clinical practice (i.e., stepwise titration) to a tolerable dose with an improvement in worst itch intensity. To facilitate evaluation by achieved dose, the dose to which the patient has been titrated at the end of Treatment Week 4 will be maintained through Study Week 50, with the exception of two allowable down-titrations (See [Table 3](#) for dosing schedule). Patients who require a third down-titration after Treatment Week 4 must be discontinued from the study.

Patients can enroll into TR03ext and receive drug as early as approximately 2 weeks following their last dose of study drug in the parent study TR03. Approximately one-third of patients are expected to enter the study after having received placebo in TR03. These patients are expected to have a high level of pruritus intensity. On the other hand, some patients who have received active treatment in TR03 may still have either reverted to their original pruritic conditions or may have a residual anti-pruritic effects from the drug treatment even following the 2-week wash out period. To allow for various starting levels of pruritus intensity, patients who have Worst Itch NRS that is ≥ 5 will enter the Treatment Period upon completion of Visit 1a. Patients whose Worst Itch NRS score is < 5 will be entered into an extended screening period, no-treatment criteria Observation Period for up to 12 weeks or until they develop a higher level of pruritus (i.e., Worst Itch NRS ≥ 5), at which point they will transition to the Treatment Period upon completion of Visit 1b. All patients entering the Treatment Period, whether immediately upon study entry or following a period of time in the Observation Period, will initially be titrated to a dose that can be as high as 180 mg BID during the first 4 weeks of the Treatment Period (See [Table 3](#) for dosing schedule). Patients who continue in the Observation Period and maintain a Worst Itch NRS score of < 5 will be screen failed from the study at the end of the 12-week period. While patients remain in the Observation Period, they will not be considered as enrolled into the study, but as participating in an extended screening process until they are eligible for treatment.

Patients, who fail to improve, as defined by the failure-to-improve criteria, will be taken off study drug treatment. A failure-to-improve criteria is implemented beginning on TV 3 and at every subsequent Treatment Visit, and is described in [Section 11.1](#). The rationale for the failure-to-improve criteria is based on the following: Following a maximal titration period of up to 3-weeks, an approximate 2-week window on stable drug dose should be sufficient for the drug to start eliciting a beneficial effect. The patient's self-reporting of pruritus intensity at each visit, beginning at TV 3, will be compared to the baseline value of the

patient's pruritus intensity upon entry to TR03ext. The premise of the failure-to-improve criteria is that patients will not be allowed to continue to receive study drug for an extended period of time if there is no demonstration of diminishment in pruritus intensity. Patients discontinued from treatment are to participate in the Washout and Safety Follow-up Period, unless consent is withdrawn. These patients will also receive a Telephone Contact 30 days (+2 weeks) post the completion of study drug to collect safety information related to previous drug exposure.

In the parent study, TR03, the two target doses (90 mg and 180 mg) of nalbuphine HCl ER are both within the dose range that was well tolerated in HD subjects and healthy volunteers subjects from study TR01 (30 mg to 240 mg BID for up to 15 days). Additionally, data from TR01 suggested a decrease in itching intensity in this dose range. Further, the safety profile of nalbuphine following injection is well documented. Injectable nalbuphine has been commercially available in the United States since 1979 and there has been marketing experience within the European Union dating back to 1986 (See Nalbuphine -Medicines Evaluation Board in the Netherlands Public Assessment Report (2010) for a recent review).

In order to facilitate analysis of the clinical safety data and efficacy data, patients in the present study will begin titration at the 30 mg QD dose and titrate to only a maintenance dose ranging between 30 mg BID and 180 mg BID. The 30 mg BID and 60 mg BID doses are believed to be only marginally effective doses based on available TR01 data. However there is a two time dose reduction permitted for all patients during Treatment Weeks 5-50 (see [Table 3](#)) to the next lower allowed dose (e.g., a patient at the 90 mg BID maintenance dose will be permitted a dose reduction to 60 mg BID or subsequently to 30 mg BID and then be maintained at that dose level for the remainder of the study).

The study population being evaluated is an intended target population for oral nalbuphine HCl ER tablets: prurigo nodularis patients.

Patients will be closely monitored for safety. All patients will be seen at the Investigator site (See Schedule of Events in [Appendix 1](#)). Adverse events and vital signs will be recorded. Additionally, 12-lead ECGs (locally and centrally read), physical examinations, and clinical laboratory testing will be conducted to monitor safety on patients receiving study drug. Safety monitoring will be done to address the primary objective of evaluating the longer term safety of study drug exposure. The primary endpoint is a description of adverse events during up to 50-weeks of treatment with nalbuphine HCl ER tablets. An important secondary endpoint objective of the study is to use recorded PAS metrics to assess the study drug anti-pruritic suppression of the scratching behavior of the patient and impact on skin lesion improvement. Changes in patient-reported outcome measures will be explored to include: Worst itch NRS, Average itch intensity NRS, VRS (itchy, burning and stinging), ItchyQoL, MOS Sleep-R, HADS and PBI-P.

9.3 SAFETY MONITORING PLAN

Patients will be closely monitored for safety. Adverse events will be continuously evaluated throughout the study (and in particular AEs of special interest: nausea, vomiting, constipation, somnolence, sedation, dizziness, and vertigo) and vital signs, locally and

central cardiac core laboratory read 12-lead ECGs, physical examinations, and clinical laboratory testing will be conducted to monitor patient safety.

An independent Data Safety Monitoring Board (DSMB) will periodically review safety data during the time period that the blinded part of the nalbuphine HCl program remains ongoing. The frequency of data review and DSMB processes are outlined in the DSMB charter.

Patients with apparent failure-to-improve to a stable dose of study drug will be taken off study drug.

As with all patients who are discontinued from study drug, the patient will complete a daily SOWS scale for the two weeks following the last dose of study drug. The SOWS is a self-administered scale for grading opioid withdrawal symptoms. If the patient is experiencing any symptoms on the SOW scale to a moderate degree, they will be instructed to contact the site. If a patient is determined to be experiencing significant subjective withdrawal symptoms (at the Investigator's discretion), they will be offered treatment.

As summarized in Section 6.2.7 of the Investigator's Brochure, the CNS has been identified as the only target organ when nalbuphine was given to animals at high doses. In addition, the most frequently reported adverse events reported in the nalbuphine HCl ER tablet dosing studies were primarily in the nervous system and gastrointestinal organ system categories.

To mitigate opioid-related side effects, nalbuphine will be titrated over 4 weeks based on tolerability to a dose that is between 30 mg BID to 180 mg BID (see [Table 3](#)). Titration is a clinical management strategy consistent with dosing of opioids in general (Jovey 2003). The titration regimen planned in this study is similar to the regimen used in study TR01, in which doses in the planned range were well tolerated ([Section 3.3.2](#)) except up-titration is not a forced titration. This will provide flexibility for each patient to assess tolerability. In this study, the combination of a low starting dosing (30 mg on the first day) followed by a relatively slow titration (dose escalation after a minimum of six consecutive doses over approximately 3 days) is expected to minimize treatment-limiting opioid adverse effects. See [Table 3](#) for the drug titration scheme. The time interval between dose escalations is consistent with the "three day tolerance check" suggested by the National Opioid Use Guideline Group of Canada (2010) for outpatient clinical practice management of opioid drug titration as part of monitoring patient side effects.

Nalbuphine has μ -opioid antagonist pharmacological properties. To minimize the possibility of acute opiate withdrawal occurring at drug initiation in a physically dependent subject, patients receiving daily doses of opiates are excluded from the study. Patients who require ongoing non-daily opiates concurrently with nalbuphine should be monitored carefully for additive opiate effects. If patients develop a new need for daily opiates during the study, the Investigator is required to contact the Medical Monitor to discuss the specifics of the situation.

It is known from prior studies, that gastrointestinal opioid-like adverse effects (e.g., nausea, vomiting, and constipation) occur early and can be treatment-limiting. In anticipation of the possible occurrence of these effects, pre-medications for nausea will be permitted and Investigators will be advised to use pharmacologic or non-pharmacologic means to avoid

constipation as clinically indicated. In anticipation of the possible occurrence of central nervous system (CNS) AEs such as somnolence, patients will be instructed to be aware of possible CNS AEs that may occur. The evening doses during the Titration Period should be taken at home. The first dose of any new titration step will occur with an evening dose (see [Table 3](#)). In order to monitor any potential CNS related side effects, a brief neurological assessment will be conducted at each study visit as well as a focused neurological medical history will be obtained at enrollment.

Patients will be additionally instructed that if any significant CNS AEs occur, they are to avoid activities such as driving and operation of dangerous machinery until the effect of the Study Drug can be assessed by the Investigator. Additionally, concomitant use of daily opioids during the course of the study, other than for short-term use, can be undertaken with the approval of the Medical Monitor. Overdoses or opioid-related significant central nervous system adverse effects may be reversed with opioid antagonists if clinically indicated.

Although psychological dependence or abuse can develop to opioid drugs when chronically administered, the risk for psychological dependence or abuse in this study is judged to be low based on previous clinical studies with nalbuphine HCl ER oral tablets. To date, there have been no reported cases of psychological dependence or abuse reported following dosing for 3 weeks up to 180 mg BID and dosing for 15 days up to 240 mg BID. See the Investigator's Brochure for details. Nevertheless, the nalbuphine HCl injection package insert for the product sold in the United States states that "*individuals with a prior history of opioid or other substance abuse or dependence may be at greater risk for the development of drug abuse and dependence*".

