
Selection Criteria
	
Exclusion Criteria:
 
If a patient meets any of the following criteria, he or she is not eligible:
 
 1. Patients with a history of congestive heart failure of Class 2 or higher as graded using the New York Heart Association scale (scale provided in Appendix 5) 2. Patients with a history of angina pectoris grade 2 or higher as graded using the Canadian Cardiovascular Society grading scale (scale provided in Appendix 5) 3. History of ventricular tachycardia, torsade de pointes, family history of sudden death, myocardial infarction or acute coronary syndrome within the previous 3 months, as reported by the patient. 4. Serum potassium below the laboratory lower limit of normality at TR03 Visit 5. Note: Potassium levels below the laboratory lower limit of normal at Visit 6/Visit 1a should be repeated and potassium supplementation provided as appropriate. 5. QTcF interval >450ms on screening/Visit 1a ECG. 6. Heart rate <50 BPM on any screening measurement. Patients with a resting heart rate of <50 bpm will have it repeated once after 5 minutes in the supine position, and if it remains <50 bpm during the repeat, they will be considered a screen failure. 7. Use of a medication known to be associated with risk of torsade de pointes (see Section 9.7.8, Safety Assessments, for hyperlink to the CredibleMeds Filtered QTDrug List for cardiovascular related prohibited medications with a known associated risk of Torsade de Pointes) 8. History of substance abuse within the past year as determined by the Investigator 9. Significant medical condition or other factors that in the opinion of the Investigator may interfere with the conduct of the study 10. Known hypersensitivity or allergy to nalbuphine or formulation components 11. Is a pregnant or lactating female

Study Treatment Allocation
	
All patients who are enrolled into the study will receive active treatment with nalbuphine HCl ER tablets.

Study Procedures
	
Visit 1a of the TR03ext study is temporally the same visit as TR03 Visit 6. Patients who do not consent by the end of the TR03 study visit 6 are no longer eligible for the extension study. Study TR03 Visit 6 procedures in

common with Study TR03ext Visit 1a procedures do not have to be repeated.

For All Patients:

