Metze et al (1999) reported that 9 out of 17 patients with PN who were treated with the mu antagonist medication naltrexone reported a decrease in pruritus intensity of at least 50%. Reduced scratching as well as skin lesion healing was reported over a time period of up to 20 months on drug. This clinical observation potentially has different anatomical locations for the mechanistic drug effect. Since Stein et al (2003) reported that inflammation increases both the number of sensory nerve terminals (“sprouting”) and disrupts the perineural barrier –thus facilitating opioid access to receptors, there is the possibility that peripherally acting mu antagonist naltrexone action reduced the neural membrane excitation by blocking actions of endogenous endorphins reported by Bigliardi and Bigliardi-Qi (2004) to be present in the epidermis. In fact, Bigliardi and Bigliardi-Qi (2004) suggest an opiate antagonist be therapeutically investigated for this reason and also comment on the evidence that mu opiate receptors on epidermal cells may be have a role in skin healing.

However, consideration must also be given to central nervous system opioid pharmacology as a contributing antipruritic effect elicited by naltrexone. At the spinal cord level, Schmelz (2005) commented that the explanation for opiate mu antagonists being capable of reversing experimentally induced itch may be related to the neurobiology of spinal cord level neuronal kappa-mu opioid gating circuits where either a mu antagonist or kappa agonist drug may act to have a pruritus suppressing effect. Supraspinal brain level action related to interference of the circuits related to reward behavior cannot be excluded given that it is known that naltrexone, like nalbuphine, can abolish morphine induced pruritus from morphine administered intrathecally. In addition, opiate receptor neuronal systems are known to be related to the physiological psychology of human reward behaviour and mu antagonist opioid class drugs are known to block the phenomena (Le Merrer et al 2009). Nalbuphine is known to block the effects of mu agonist drugs and induce the opioid withdrawal syndrome (Nubain® label).

3.1.3.3 *Nalbuphine Clinical Data in Uremic Pruritus*

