 - VRS
 - ItchyQoL
 - MOS Sleep-R
 - HADS
 - record AEs
 - record concomitant medications
 - If the Worst Itch NRS is greater than or equal to 5 (≥ 5), transition the patient to the Treatment Period and conduct Visit 1b procedures (described in [Section 9.6.4](#)) on the same day as this visit. See [Table 8](#) for a summary related to future Treatment Period Visits.

Patients whose Worst Itch NRS is less than 5 (<5) at the OV4 should be screen failed from the study. No Washout/Safety follow-up visit is to take place.

9.6.3.3 *Transitioning from the Observation Period to the Treatment Period*

- For patients who have a Worst NRS score that is greater than or equal to 5 (≥ 5) at Observation Visit 2, 3, or 4, complete Visit 1b procedures (see [Section 9.6.4](#)).
- These patients will receive up to 46 weeks of study medication treatment.
- See [Table 8](#) for the Treatment Period Visits to be completed post Visit 1b, as well as the number of weeks of study drug to dispense at each Treatment Visit and when to schedule the End of Treatment Visit 14 (TV14) to take place.
- See [Section 9.6.2](#) and the Schedule of Events ([Appendix 1](#)) for procedures to be performed at each applicable Treatment Visit.

9.6.4 **Transition to Treatment Period (Visit 1b)**

Confirm each patient's eligibility (see [Sections 8.2](#) and [8.3](#)) prior to performing any Visit 1b procedures. If the patient does not meet eligibility requirements, do not perform any Visit 1b procedures; the patient is to be screen failed.

See [Table 4](#) for summary of Visit 1b procedures.

Patients evaluated at OV 2-4 who record a Worst itch NRS greater than or equal to 5 (≥ 5) and, are otherwise eligible, can immediately begin Visit 1b and transition into the Treatment Period. The following procedures are to take place at this visit:

- obtain vital signs
- conduct a physical examination
- collect central laboratory samples (hematology and chemistry)
- collect serum pregnancy test sample in women of childbearing potential (regardless of sexual activity) and send for processing at the central laboratory*
- collect urine for central lab urinalysis
- urine for pregnancy test (regardless of sexual activity) and confirm negative status prior to dispensing study drug*

* If the urine pregnancy test result is negative and the serum pregnancy test result is positive, the patient is to be contacted and the following actions are to take place:

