Appendix 1: Schedule of Events

Table 4: Schedule of Events for Visits 1a and 1b (Day 1 of Week 1 of Treatment Period)		
Visit	1a¹	1b⁴
Informed Consent ²	X	
Confirm Eligibility	X	
Vital Signs ³	X	X
Physical Examination	X	X
Neurological Exam	X	X
Central Clinical Labs ⁵ & serum Pregnancy Test ⁶	X	X
Urinalysis	X	X
Urine for pregnancy test ¹¹	X	X
Blood for PK	X	X
Perform skin biopsy (only at select sites and the procedure is optional) ⁹	X	X
12-lead ECG ¹²	X	X
Worst itch Numerical Rating Scale (NRS) ⁷	X	X
Average itch intensity Numerical Rating Scale (NRS) ⁷	X ⁹	X
Verbal Rating Scale (VRS) ⁷	X ⁹	X
ItchyQoL ⁷	X ⁹	X
MOS Sleep-R ⁷	X ⁹	X
Hospital Anxiety and Depression Scales (HADS) ⁷	X ⁹	X
Patient Benefit Index Pruritus (PBI-P) ⁷	X ⁹	X
Prurigo Activity Score (PAS)	X ⁹	X
Record AEs	X	X
Review Rescue Medications and Concomitant Medications	X ⁸	X
Retrieve TR03 study drug	X	
Dispense Study Drug for TR03ext ¹³	X ⁹	X
Collect Rescue Medication Log for TR03	X	
First dose of Study Drug for TR03ext ^{10,13}	X ⁹	X
Dispense Drug Dosing Instructions and Dosing Diary	X	X
Dispense TR03ext Rescue Medication Log	X	X

¹Visit 6/1a procedures in common do not have to be repeated if visits are performed on the same day.

²To be completed any time before start of Visit 1a procedures

³BP and HR (sitting or semi-recumbent), RR, temperature. Height, weight, and BMI at Visit 1a only.

⁴Visit 1b is the first visit of the Treatment Period for patients transitioning from the Observation Period to the Treatment Period.

⁵Hematology and chemistry

⁶Females of Childbearing potential only

⁷Questionnaires must be administered strictly adhering to instructions (see Study Reference Manual)

⁸Includes review of patient TR03 Rescue Medication Log

⁹Study procedures only conducted if patient qualifies to enter the Treatment Period based on Worst itch NRS ≥ 5

¹⁰Titrate study drug according to the schedule in [Table 3](#);

The first dose of study drug treatment will define enrollment into the study

¹¹For female patients of child-bearing potential, a urine pregnancy test must be negative prior to dispensing study drug.

¹²ECGs are to be performed after the patient has been in the supine position for at least 5 minutes. ECGs will be read by the Investigators for clinical significance and centrally by a core ECG laboratory for analytical and DSMB safety review

¹³The first dose of study drug is to be taken in the evening, see [Section 9.7.1](#) and [Section 9.3](#)

Table 5: Treatment Weeks 2-4

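### Section 9.3 bars daily opiate users to prevent withdrawal at first dose, but no listed eligibility criterion does so

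*Protocol*

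**What the plan says.** Section 9.3 (Safety Monitoring Plan) notes nalbuphine's mu-antagonist action, gives acute withdrawal in a dependent patient as the hazard at initiation, and states the safeguard as fact: "patients receiving daily doses of opiates are excluded from the study". Non-daily opiates are allowed with careful monitoring. For needs that arise later it adds: "If patients develop a new need for daily opiates during the study, the Investigator is required to contact the Medical Monitor". Section 3.1.3.2 describes the hazard directly: "Nalbuphine is known to block the effects of mu agonist drugs and induce the opioid withdrawal syndrome".

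Section 8.1 defines the study population as TR03 completers who "have met all Inclusion and Exclusion criteria for TR03ext", citing Sections 8.2 and 8.3. The only medication criterion in 8.3 is number 7, "Use of a medication known to be associated with risk of torsade de pointes". Number 8, which also appears in the synopsis, is "History of substance abuse within the past year as determined by the Investigator". Number 9 leaves other conditions or factors to the investigator's opinion.

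For patients coming from the Observation Period, Section 9.6.4 requires eligibility to be confirmed against 8.2 and 8.3, and says: "If the patient does not meet eligibility requirements, do not perform any Visit 1b procedures". In Table 4 (Appendix 1) the row "Confirm Eligibility" is marked for Visit 1a and left blank for Visit 1b.

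**The concern.** An exclusion works only if it is in the list that the site checks. Here the protocol names a hazard, chooses a safeguard and treats it as in force, but the governing lists do not carry it. A prescribed daily opiate is not substance abuse. It is a torsade drug only if it happens to be on that list, and under criterion 9 it is a matter of judgement, whereas Section 9.3 is categorical.

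What is at stake is safety at treatment start. A patient dependent on a prescribed opiate could pass every listed criterion and then take nalbuphine unsupervised at home.

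**Working it through.** No figure in the protocol has to be reproduced. The check compares sections and then works out two intervals and one dose conversion.

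**1. Criteria that name opiates or opioids**

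| List | Criteria | Naming opiates |
|---|---|---|
| Section 8.2, inclusion | 5 | 0 |
| Section 8.3, exclusion | 11 | 0 |
| Synopsis, inclusion | 6 | 0 |
| Synopsis, exclusion | 11 | 0 |

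That is 0 of 5 + 11 = 16 in the body and 0 of 6 + 11 = 17 in the synopsis.

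**2. Do other rules act before the first dose?**

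- Section 9.7.6.3 asks for contact with the Medical Monitor about daily opioid treatment, but that sentence is worded for patients already enrolled. Table 4, footnote 10, defines enrolment by the first dose, and Section 9.2 says Observation Period patients are not enrolled.
- The Medical Monitor duty in Section 9.3 is not limited to enrolled patients, but making contact is not a bar to dosing.
- Section 9.7.6.2 and Tables 4 and 7 have medications recorded from consent, at Visits 1a and 1b and at OV2 to OV4. An opiate would be seen, but no listed criterion tells the site to act on it.
- The Visit 1a and 1b procedures and Table 4, footnote 13, refer to Section 9.3, but for CNS events and evening dosing.

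**3. Time in which a daily opiate could be started**

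Inputs: Visit 1a falls from about 14 days after the last TR03 dose (Section 9.2) to at most 30 days (Section 9.6.1). OV2, OV3 and OV4 are at weeks 4, 8 and 12, that is 28, 56 and 84 days, each ±3 days (Table 7).

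| Route | Days since Visit 1a | Days since last TR03 dose, nominal | With ±3 days |
|---|---|---|---|
| Direct entry | 0 | 14 to 30 | not applicable |
| OV2 | 28 | 14 + 28 = 42 to 30 + 28 = 58 | 39 to 61 |
| OV3 | 56 | 14 + 56 = 70 to 30 + 56 = 86 | 67 to 89 |
| OV4 | 84 | 14 + 84 = 98 to 30 + 84 = 114 | 95 to 117 |

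These are opportunities for change, not risks. The days before Visit 1a normally fall within TR03, whose medication rules are not shown. The days since Visit 1a are the part that belongs to this protocol.

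**4. Exposure before the next scheduled contact**

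The first dose is 30 mg in the evening at home (Sections 9.6.1 and 9.6.4). The recommended Week 1 schedule reaches 60 mg on the evening of Day 5 and 60 mg twice daily on Days 6 and 7. The next scheduled contact is TC1 in Treatment Week 2. With the roughly 6-fold oral-to-IV ratio in Section 9.4:

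- 30 mg oral ÷ 6 = about 5 mg IV
- 60 mg oral ÷ 6 = about 10 mg IV, the usual parenteral dose quoted there

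The withdrawal scale (SOWS) is scheduled at TV14, daily in the washout and at early termination (Table 6). It would not record withdrawal at initiation.

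**The case against.** The strongest reply is that the exclusion exists. Section 9.3 is operative protocol text, so the defect is a rule not repeated in a list, and a careful site would apply it. Inclusion criterion 4 in Section 8.2, a general willingness to comply with the study's rules, arguably brings in restrictions stated elsewhere. Section 9.7.6.2 tells patients not to start new medicines without consulting the investigator, and this covers the Observation Period. In Section 9.7.6.3, the caution about starting opiates and the rule to stop when more than 2 weeks' use is expected are not limited to enrolled patients. The starting dose is also low, about 5 mg IV equivalent.

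Some of this stands. The rule is misplaced rather than absent, the intervals in the table do not measure risk, and the low first dose and slow titration temper the hazard. But criterion 4 is generic. The advice on new medicines creates no bar to entry and does not reach an opiate already in use at consent. The rules in Section 9.7.6.3 govern opioids introduced during the study; they do not screen a current user. The low starting dose does not settle the matter either, because the recommended schedule reaches the usual parenteral equivalent within Week 1, and the sponsor chose exclusion as well as slow titration.

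TR03 may have excluded daily opiate users. Even so, that would not cover an opiate started afterwards.

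**Conclusion.** The concern holds as an internal inconsistency that should be fixed. Section 9.3 asserts a categorical exclusion, and 0 of 16 criteria in the body and 0 of 17 in the synopsis carry it. The Visit 1b check cites only the lists that omit it.

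The number of patients at risk cannot be determined from the document. Within this protocol, the time for a new daily opiate to begin between Visit 1a and first dose runs from none at direct entry to about 84 days via OV4. The finding does not rest on these intervals, and the long ones apply only to Observation Period patients. The primary endpoint is unaffected.

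Three lesser points go with it:

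- The blank Visit 1b cell in Table 4 is a schedule slip, since Section 9.6.4 already orders the check.
- Section 11.2 cites Section 9.7.8 for the opioid rule, which is in 9.7.6.3.
- Section 9.3 lets daily opioids beyond short-term use continue with Medical Monitor approval and no time limit, while 9.7.6.3 and 11.2 call for discontinuation if more than 2 weeks is expected. Because short-term is not defined, the two can be reconciled only if approval stops at 2 weeks, and the text does not say so.

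**What to change.** Add current daily opiate use as an exclusion criterion in Section 8.3 and the synopsis, confirmed from the concomitant medication review at Visit 1a and again at Visit 1b before study drug is dispensed. Limit it to daily use, because Section 9.3 permits monitored non-daily opiates. Mark the eligibility row for Visit 1b in Table 4 to match Section 9.6.4.

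In the same amendment, limit the Medical Monitor approval in Section 9.3 to daily opioid use of 2 weeks or less, and change the reference in Section 11.2 from 9.7.8 to 9.7.6.3.

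The cost is amendment wording and one mark in a table. No procedure is added, because medications are already reviewed at both visits.
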